4.2.2 Safety

- The incidence, frequency, and severity of adverse events related to treatment with the device will be reported.
- <5% rate of serious adverse events related to the device or procedure (as determined by the site PI). Serious adverse events are classified in the Adverse Events table (page 25)

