4 STUDY DESIGN

4.1 General Description

This study is a multi-center, randomized, open-label clinical trial evaluating the efficacy and safety of ESG as an adjunct to life-style intervention for weight loss and improvement in obesity-related co-morbidities compared to lifestyle intervention alone in participants with a BMI ≥ 30 and ≤ 40 kg/m² who have failed to achieve and maintain weight loss with a non-surgical program.

Participants will be recruited from outpatient clinical weight loss clinics and from study-related institutional review board (IRB) approved advertisements. The cohort will include nor more than 50 patients without at least one of a) hypertension (HTN) on one or more anti-hypertensive medications or b) type II diabetes mellitus (DM) on oral agents only with HbA1c ≤ 9 . Enrollment will be tracked continuously and enrollment closed to non-DM, non-HTN patients after meeting the target for that group.

Two hundred eligible participants will be stratified into three groups (obesity, obesity-hypertension, and obesity-diabetes) and then block-randomized 1 to 1.5 to treatment (80 participants) and control (120 participants) groups alone as depicted in the diagram on page 16. All treatment group participants will undergo endoscopy and those without endoscopic contraindications will undergo the ESG. All control subjects will follow a low-calorie, healthy lifestyle intervention only for 12 months. After 12 months of lifestyle intervention, eligible control participants will crossover to receive the ESG. Those who had the ESG will undergo a repeat upper endoscopy at 52 weeks +- 4 weeks to evaluate the durability of the plications and re-tighten the ESG if needed with continued follow-up for 12 additional months.

The study will have two levels:

1. Level 1: the randomized study phase with primary outcomes for both groups evaluated at 12 months
2. Level 2: the crossover, non-randomized study phase with outcomes for a) the initial treatment group at 24 months post ESG (12 months after the re-tightening procedure) b) for the controlled cross-over group evaluated at 12 months after ESG

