	Enrollment; Screening/ Baseline	Randomization / Week 1 visit	Weeks 4, 8	Week 12	Weeks 16, 20	Week 24 (6 month)	Weeks 30, 36, 42, 48	Week 52 (Final Year 1 visit), re-screen for crossover to ESG	Unscheduled Visit
Visit Number	-1	1	2,3	4	5,6	7	8,9,10,11,	12	
Informed consent	X								
Complete Physical Exam (CPE) by Investigator or Investigator delegated / medically qualified team member	X			X		X	X	X	X
Investigator or Investigator delegated/medically qualified team member exam		X ⁺⁺	X	X	X	X	X	X	X
EKG if (> 50 yo)	X							X	
Formal nutritional assessment	X								
Formal psychology evaluation	X								
Pregnancy test (females of childbearing potential only)	X								
Laboratory tests, H-pylori breath testing (baseline only)* *	X							X	
Questionnaires#	X			X		X		X	
Inclusion/exclusion criteria	X							X	
Endoscopy / Procedure									
Procedure Assessment Form									
GERD Questionnaire + Activity Assessment Form	X	X	X	X	X	X	X	X	
Weight, BMI/height, Waist and Hip Circumference Form	X	X	X	X	X	X	X	X	X
Vital Signs Form	X	X	X	X	X	X	X	X	X
Adverse Events Form		X	X	X	X	X	X	X	X
Medications Form##	X	X	X	X	X	X	X	X	X
Post-enrollment Nutrition / Exercise / satiety counseling and assessment		X	X	X	X	X	X	X	
Randomization to ESG vs. LS ⁺		X							
Subject Satisfaction Questionnaire (control phase)								X	

** Electrolytes, Creatinine, CBC, Iron, TIBC, B12, 25-hydroxy Vitamin D, TSH, HgA1c, fasting blood sugar and insulin, PTT, fasting lipids profile (total cholesterol, LDL, HDL, and Triglyceride), ALT, AST, ALK-P, total bilirubin, direct bilirubin, BUN, total protein, albumin, CRP, urinalysis; also include PYY-1, GLP-1 and total Ghrelin pending sites' availability to analyze

Eating disorder questionnaire + hospital anxiety and depression questionnaires (only at base-line), IWFQOL-Lite, SF36, PHQ9, Pittsburgh Sleep Quality Index (PSQI), Three factor eating questionnaire (TFEQ)

Record all medications including dose and frequency; especially diabetes and blood pressure medication.

+ LS start with the week 1 visit with no transitional diet.

++ Required only for Week 1 visit

5.6.1.1.4 Schedule of Events for Control Group, Crossover in Year 2, Level 2

[figure not shown]
TABLE 3. MERIT SCHEDULE OF EVENTS (Year 2, Level 2, Control Group, cross-over 120 patients)									
	ESG Procedure	Post-Op Phone Call	Weeks 1, 4, 8	Week 12	Weeks 16, 20	Week 24 (6 month)	Weeks 30, 36, 42, 48	Week 52 (Final Year 1 visit)	Unscheduled Visit
Visit Number	0	-	1,2,3	4	5,6	7	8,9,10,11	12	

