6.2 Adverse Events

6.2.1 Definitions

The following definitions will be used:

6.2.1.2 Adverse Event:

Any untoward medical occurrence, unintended disease or injury, or untoward clinical signs (including abnormal laboratory findings) whether or not related to the study intervention. Each subject will be followed closely to ensure safety.

Adverse events will be classified using the Clavien-Dindo classification.

Grade	Definition
Grade I	Any deviation from the normal postoperative course without the need for pharmacological treatment or surgical, endoscopic, and radiological interventions Allowed therapeutic regimens are: drugs as antiemetics, antipyretics, analgetics, diuretics, electrolytes, and physiotherapy. This grade also includes wound infections opened at the bedside
Grade II	Requiring pharmacological treatment with drugs other than such allowed for grade I complications Blood transfusions and total parenteral nutrition are also included
Grade III	Requiring surgical, endoscopic, or radiological intervention
Grade IIIa	Intervention not under general anesthesia
Grade IIIb	Intervention under general anesthesia
Grade IV	Life-threatening complication (including CNS complications) requiring IC/ICU management
Grade IVa	Single organ dysfunction (including dialysis)
Grade IVb	Multiorgan dysfunction
Grade V	Death of a patient

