6.2.1.2.1 Treatment Criteria

6.2.1.2.1.1 Thiamine Replacement

Criteria for thiamine replacement for suspected or established vitamin B₁ deficiency on subjects with uncontrolled nausea and/or vomiting:

- Vomiting post ESG continues 7 days or more after EGS, in ability to take down adequate levels of hydration. Defined as vomiting >2 x a day.
- Nausea post ESG continues 7 days, daily with the inability to drink due to nausea, unrelieved by nausea medication, and continuing 7 days or more.

Thiamine replacement²⁶:

- Hospitalization: 500 mg per day thiamine IV push for 3-5 day followed by 250 mg per day IV push + multivitamin in 1 L NS q day while in the hospital.
- Outpatient: Thiamine 100 mg TID daily for 3 months.

6.2.1.3 Serious Adverse Event (SAE):

An adverse event that meets one of the following criteria

- Led to death
- Resulted in serious deterioration in the health of the subject that results in:
 - Life-threatening illness or injury
 - Permanent impairment of a body structure or a body function

- The need for in-patient care or prolongation of hospitalization (this does not include the optional 23 hours observation admission after ESG or re-tightening procedure).
- Medical or surgical intervention to prevent life-threatening illness or injury or permanent impairment to a body structure or a body function.
- **Planned hospitalization for a pre-existing condition, or a procedure required by the trial protocol, without serious deterioration in health, is not considered a serious adverse event**

Unanticipated problems, SAEs and AEs will be reported to governing IRBs per local guidelines.

6.2.1.4 Device-Related Adverse Event (DRAE):

An adverse event related to the use of the medical device. This definition includes any events resulting from incorrect delivery and operation of the device and/or of its approved accessories, or any malfunction of the device or its components. This definition also includes any event resulting from user error or from intentional misuse of the device.

6.2.1.5 Serious Device-Related Adverse Event (SDRAE):

Any untoward medical occurrence that can be attributed wholly or partly to the device, which resulted in any of the characteristics of a serious adverse event as described above.

6.2.1.6 Unanticipated Adverse Device Effects (UADE):

Any adverse device effect which by its nature, incidence, severity or outcome, has not been identified under the SAE section 6.2.

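### Both safety endpoints count only device- or procedure-related events, and the plan commits to no between-arm comparison of adverse events although all-cause events are recorded in both arms

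*Combined protocol and SAP*

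**What the plan says.** Section 4.1 describes a trial "evaluating the efficacy and safety of ESG as an adjunct to life-style intervention for weight loss", with lifestyle intervention alone as the comparator.

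Section 4.2.2 lists two safety endpoints:
- The first is descriptive. It looks at how often events occur and how severe they are, but only for a restricted set: "adverse events related to treatment with the device will be reported". No comparison between arms is named.
- The second is a threshold to be met, "<5% rate of serious adverse events related to the device or procedure (as determined by the site PI"), a single rate with no comparator.

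Section 6.2.1.2 defines adverse events much more widely, "whether or not related to the study intervention". In the section 5.6 schedules the "Adverse Events Form" is marked at every Level 1 follow-up visit through week 52 in both arms. It starts at the randomization/week 1 visit for controls and at the procedure for ESG patients.

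On analysis, section 7.2.3 says in permissive terms that safety endpoints and adverse events can be looked at by treated group, with per-protocol in brackets. Section 7.2.2 plans a chi-square test of esophagitis between arms. Section 7.5 has adverse events monitored and discussed with the data monitoring committee. No other part of section 7 addresses adverse events.

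**The concern.** A safety aim stated against a comparator needs an analysis that uses the comparator. The endpoints filter events by attribution to a device that one arm does not have. The control count is then zero by construction, and what remains is a one-arm figure that depends on the site investigator's judgement in an open-label trial.

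An all-cause comparison by randomized arm does not depend on that judgement. It is the natural way to detect an excess of events that nobody links to the procedure. If it is not pre-specified, section 7.2.3 itself classes it as exploratory and post hoc.

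The one sentence that could cover it points to the per-protocol set, which the same section defines by receipt of the procedure and attendance at 80% or more of visits. Read literally, that could drop patients who stopped attending, possibly because of an adverse event.

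**Working it through.** **1. Can the stated endpoints compare the arms?**

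| Element | Section | Events covered | Between-arm use committed? |
|---|---|---|---|
| Safety endpoint 1 | 4.2.2 | Device-related | No; descriptive |
| Safety endpoint 2 | 4.2.2 | Device- or procedure-related SAEs | No; one rate against 5% |
| Safety analysis sentence | 7.2.3 | Safety endpoints and adverse events | No; optional, by treated group |
| Esophagitis test | 7.2.2 | Esophagitis | Named, but see step 2 |
| AE definition | 6.2.1.2 | All causes | Not an analysis |
| AE form | 5.6 | All causes, both arms to week 52 | Not an analysis |

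The data for an all-cause comparison are scheduled. No row commits to making one.

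**2. Does the esophagitis test fill the gap?** No. The Level 1 control schedule has no endoscopy. Section 4.2.1 ties this outcome to the repeat endoscopy at 12 months, which section 5.5.1.1.2 limits to ESG patients who have not exceeded 25% EWL. It covers one condition and lacks scheduled Level 1 control data.

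**3. Are the two arms' records aligned?** Not fully.
- The control form starts on the day of randomization. The ESG form starts at the procedure, which section 5.4 allows up to 30 days later.
- Laboratory tests at week 24 are scheduled in the ESG arm only; both arms have them at baseline and week 52.

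**4. How precise would the comparison be?** The documents give arm sizes of 80 and 120 (section 7.1) and a 2% SAE incidence in an earlier ESG series (section 2.2). They give no control SAE rate and no safety sample size, so there is no plan figure to reproduce. The counts below are purely hypothetical.

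Take 4/80 against 2/120. The difference is 0.0500 - 0.0167 = 0.0333. Wilson 95% limits, [p + z²/2n ± z√(p(1-p)/n + z²/4n²)] / (1 + z²/n) with z = 1.96, are:
- ESG: 1.96% to 12.16%
- Lifestyle: 0.46% to 5.87%

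Newcombe limits, in points:
- Lower: 3.33 - √[(5.00 - 1.96)² + (5.87 - 1.67)²] = 3.33 - 5.19 = -1.9
- Upper: 3.33 + √[(12.16 - 5.00)² + (1.67 - 0.46)²] = 3.33 + 7.26 = 10.6

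The same method for other hypothetical counts:
- 2/80 against 2/120: 0.8 points (-3.7 to 7.1)
- 4/80 against 0/120: 5.0 points (0.7 to 12.2)

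Power of Fisher's exact test at two-sided 0.05, by summing binomial probabilities over tables with p ≤ 0.05 and the higher rate in the ESG arm:

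| Assumed ESG rate | Assumed lifestyle rate | Power |
|---|---|---|
| 5% | about 0% | 57% |
| 5% | 1% | 33% |
| 5% | 2% | 17% |
| 12% | 2% | 80% |

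This supports an estimate with an interval, not a powered test.

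**The case against.** The strongest reply is that the trial's formal safety question is single-arm. Objective 1 asks whether ESG meets the societies' threshold, and section 2.3 puts that at an SAE incidence of 5% or less for the intervention. On that view, comparative safety rests on one general design sentence. This is a good reason to keep the threshold endpoint. It does not remove the aim in section 4.1, or explain why all-cause events are collected from 120 controls with no committed analysis.

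A reader might infer more than the documents support:
- *That adverse-event reporting as a whole is confined to device-related events.* It is not. Section 6.2.1.3 states "Unanticipated problems, SAEs and AEs will be reported to governing IRBs per local guidelines", the committee reviews adverse events throughout, and in section 6.1.1 the Grade III and Grade IV limits carry no relatedness condition. Only the endpoints are restricted.
- *That control data go unused.* They can reach IRBs and the committee, and section 7.2.3 leaves room for evaluation by treated group. These are oversight or options, not a commitment to a trial result.
- *That the trial can give no randomized answer on safety.* The contrast can be computed from the scheduled data. What is missing is pre-specification.

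Reflux questionnaires at follow-up visits, and laboratory tests at baseline and week 52, are also scheduled in both arms. They provide some information that needs no attribution, but section 7 specifies no safety analysis of them. The low precision in the working is a fair limit on what the added comparison can deliver.

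**Conclusion.** The point holds as a gap in the pre-specified analysis. Neither safety endpoint can compare the arms before crossover, and the plan commits to no between-arm summary of AEs or SAEs despite a stated comparative safety aim.

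Its effect on the trial's conclusions cannot be put in figures, because no control event rate is given. The hypothetical counts show only precision: intervals about 11 to 12 points wide. Most would not exclude zero at the assumed rates where power is below one half.

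The conclusion rests on the text of sections 4.1, 4.2.2, 5.6, 6.2 and 7.2, not on any assumed rate. The change should be made, but the gap does not undermine the primary efficacy analysis.

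**What to change.** Keep the device- or procedure-related 5% SAE threshold as it is. In sections 4.2.2 and 7.2.3 add:
- A descriptive summary of all AEs and all SAEs, whatever the attributed cause, by randomized arm and Clavien-Dindo grade. It should run from randomization to the week-52 visit and stop before any crossover or re-tightening.
- For SAEs, a risk difference with a 95% score-type interval such as Newcombe, because events will be few. Label it an estimate, not a powered test.
- A statement of the denominator, since the modified intent-to-treat rule in section 7.2 is written for efficacy only.

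Have the ESG visit-0 AE form cover the time since randomization, so that both arms start at the same point. Flag AEs found only on the week-24 laboratory panel, which controls do not have.

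The cost is a few extra tables and a small change to the visit-0 look-back. The estimate will be imprecise. Because the trial is open-label, events may be sought or reported differently in the two arms, and the report should say so.

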2.3 Rationale

A joint task force convened by the ASGE and the ASMBs defined safety of efficacy threshold that endoscopic bariatric therapies, such as ESG, need to meet before societies recommend their wide-spread adoption. These thresholds are as follows: EBTs intended as a primary obesity intervention in patients with mild to moderate obesity should achieve a mean minimum threshold of 25% excess weight loss (%EWL) measured at 12 months (calculated based on an ideal BMI of 25mg/kg²). In addition to the absolute threshold of weight loss, the mean %EWL difference between the procedure and control should be a minimum of 15% EWL and be statistically significant. Finally, the risk associated with EBT should equate to a 5%

incidence of serious adverse events or less. Based on this consensus statement, an endoscopic intervention that meets these established thresholds should be considered appropriate to incorporate into wide-spread clinical practice presuming that the appropriate training and credentialing in that EBT has been achieved^{24, 25}.

Despite the excellent clinical experience with ESG, no randomized clinical trials have been performed to evaluate the long-term efficacy of the technique over life-style intervention in producing significant long-term weight loss, improving obesity associated co-morbidities, and meeting the societal thresholds. Furthermore, Level 1 evidence is needed to further advance this promising technique and achieve wide-spread adoption. Therefore, we are proposing a randomized controlled trial to evaluate the long-term safety and efficacy of ESG in meeting efficacy endpoints set forth in a consensus statement by relevant societies (American Society of Gastrointestinal Endoscopy [ASGE] and American Society of Metabolic and Bariatric Surgery [ASMBS]) and its impact on obesity related co-morbidities in patients with obesity and body mass index (BMI) between 30-40 kg/m².

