3 STUDY OBJECTIVES

1. Assess if ESG achieves safety and efficacy threshold as defined by joint societal consensus statement by ASGE and ASMBS
2. Assess the impact of ESG on obesity related co-morbidities (Hypertension and Diabetes)
3. Assess the mid-term durability of weight loss achieved by ESG at 24 months.
4. Assess the impact of re-tightening the ESG on weight loss trajectory.

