ESG patients will undergo a standard moderate intensity life-style intervention administered over 12 visits in the first year after ESG. Participants will be required to follow up with their prescribing physician to make any necessary changes to their hypertension and/or type II diabetes medications at 3, 6, 9 and 12 months. Completion of patient follow-up with providers for medication adjustment will be captured with completion of the appropriate CRF at the corresponding visits. In the event that participants are unable to contact their physician or participants are experiencing symptoms related to the medication dosing requiring urgent action, the study team will make any necessary

changes in their medication dosing and document these changes appropriately in the relevant CRFs. Any medication changes will be monitored and recorded by the study team.

All ESG patients in Level 1 (80) will be evaluated for %EWL at the end of Level 1 (measurement of primary endpoint). Those ESG patients who have achieved >25% EWL at the end of Level 1 will not undergo a repeat endoscopy and will continue to follow-up with a lifestyle intervention in Level 2. Those ESG patients who have not achieved >25% EWL at the end of Level 1 will undergo a repeat upper endoscopy at 52 to 60 weeks to assess the durability of the plications (see Plication Durability form), and perform a retightening of the ESG if needed. The need for re-tightening will be determined by the PI after evaluating the sutures based on a grading system presented in the retightening CRF. The retightening procedure will be performed if at least one of the three portions (proximal, mid, and distal) of the endoscopic sleeve is non-tubular in shape. For each tubular third of the sleeve, 1 point will be given. A score of 3/3 means the entire (proximal, mid, and distal) sleeve is tubular in shape. A score of 2/3 means that one-third of the sleeve is no longer tubular. A score of 1/3 means that two-thirds of the sleeve are no longer tubular. Finally a score of 0/3 means the entire sleeve is no longer tubular. Re-tightening will occur for patients with a score of 0, 1 or 2.

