The retightening procedure will be performed in a similar fashion as the initial ESG with similar technique, peri-procedural care, transitional diet, and aftercare. However, the retightening procedure will only target open (non-restrictive) portions of the ESG; it should thus be an abbreviated procedure. The number of sutures used in the retightening procedure will be determined by the PI with the goal of re-capturing the tubular configuration of the sleeve.

All patients will continue follow-up with a modified lifestyle intervention program administered over 6 visits in the second year. Laboratory testing will be obtained as detailed in the study schedule of events (Appendix F).

Participants randomized to the ESG group will follow the same follow-up schedule as control participants in Level 1. Participants will receive \$100 for every 4 visits they attend consecutively in Level 1 with the ability to earn a maximum of \$300 at the end of the first 12 months of Level 1. In Level 2, participants will report for 6 visits, with the potential to earn \$100 for every 2 consecutive visits they attend. If they attend all 6 visits, they will receive a bonus of \$300 at the final visit, for a potential total earned of \$900 for all visits across two years.

Participants will return for follow-up visits per the schedules of events below (Appendix F). An in-window visit will be considered as reporting for follow-up visits within a two-week window of the visit date.

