6 DATA MONITORING AND SAFETY REPORTING

6.1 Data Monitoring Committee

An independent Data Monitoring Committee (DMC) will serve as an autonomous advisory group for the trial. The DMC will be responsible for safeguarding the interests of trial participants, assessing the safety and efficacy of the interventions during the trial, adjudication of Adverse Events, and for monitoring the overall conduct of the clinical trial. The DMC may also provide recommendations about stopping or continuing the trial. To contribute to enhancing the integrity of the trial, the DMC may also formulate recommendations relating to the selection/recruitment/retention of participants, their management, improving adherence to protocol-specified regimens and retention of participants, and the procedures for data management and quality control.

The DMC members appointed for this trial consist of individuals who collectively have experience and expertise in the management of patients with obesity, experience in randomized clinical trials with endoscopic devices, experience in safety monitoring and absence of significant conflicts of interest or participation in the trial.

The first DMC meeting will occur once 25 participants have undergone the ESG. Subsequent DMC meetings will be scheduled every four months while the trial is actively going.

The DMC will be led by [name], a world leader in bariatric and metabolic surgery at Florida International University and past president of the International Federation of Bariatric Surgery.

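### The <5% related-SAE endpoint uses relatedness as judged by the unblinded site PI, and the plan does not say how the independent DMC's adjudication of adverse events bears on it

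*Combined protocol and SAP*

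**What the plan says.** Section 4.2.2 (Safety) gives one numerical criterion: "<5% rate of serious adverse events related to the device or procedure (as determined by the site PI"). It states no denominator, time window or confidence limit.

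Section 6.1 (Data Monitoring Committee) describes the committee thus: "An independent Data Monitoring Committee (DMC) will serve as an autonomous advisory group for the trial". Its listed duties include "assessing the safety and efficacy of the interventions during the trial, adjudication of Adverse Events". Section 7.5 adds only that adverse events are monitored and discussed with the committee.

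Other relevant statements:

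- **Blinding.** Section 4.1: "This study is a multi-center, randomized, open-label clinical trial".
- **Sites.** Section 4.3 plans nine US centers.
- **The PI's part in the procedure.** Section 5.5.1.1.2: "The need for re-tightening will be determined by the PI after evaluating the sutures", and "The number of sutures used in the retightening procedure will be determined by the PI".
- **Standing of the threshold.** The first objective in section 3 is "Assess if ESG achieves safety and efficacy threshold as defined by joint societal consensus statement by ASGE and ASMBS". Section 2.3 paraphrases the societal safety limit as an SAE incidence of 5% or less and mentions no relatedness judgement by a site.

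**The concern.** Two assessors are named and no rule connects them. Section 4.2.2 names the site PI for the endpoint. Section 6.1 gives adjudication to the DMC without saying whether that means grade, seriousness, relatedness or all three. If the DMC disagreed with a site about whether an SAE was related, 4.2.2 read literally would still count the site's answer.

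The site PI knows the treatment and has a part in delivering it. Nine sites may also apply different standards, because the documents give no criteria for relatedness. At stake is one of the three societal thresholds in section 2.3, the other two being mean %EWL and the %EWL difference from control. A favourable result on a threshold decided by a handful of attribution calls is less convincing if the less independent of two available assessors made those calls.

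**Working it through.** The plan derives no figure for the <5% criterion, so there is none to reproduce. The check is how many events separate a pass from a fail, and what under-attribution would do if it happened.

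**Inputs**

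- Criterion: k/n < 0.05 (4.2.2). Societal limit: k/n ≤ 0.05 (2.3).
- n = 80 randomized to ESG (7.1). This is an assumption, since 4.2.2 gives no denominator.
- n = 157 as an alternative: 80 plus the 77 control participants expected to be offered ESG (7.1: 120 × 0.8 × 0.8 = 76.8). This assumes that all of them are treated and counted.
- Prior SAE incidence of 2% (2.2). All other true rates below are assumptions.

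**Step 1: where the verdict turns**

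| n | Largest k that passes <5% | Smallest k that fails <5% |
|---|---|---|
| 80 | 3/80 = 3.75% (exact 95% CI 0.78% to 10.57%) | 4/80 = 5.00% |
| 157 | 7/157 = 4.46% (exact 95% CI 1.81% to 8.97%) | 8/157 = 5.10% |

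Four of 80 fails 4.2.2 but meets the limit in 2.3, where the 5th event would be the first to fail.

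**Step 2: how often the count falls on the margin**

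P(X = k) = C(n,k) p^k (1−p)^(n−k), where k is the smallest failing count:

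| True rate p | n = 80, k = 4 | n = 157, k = 8 |
|---|---|---|
| 2% | 5.4% | 1.0% |
| 3% | 12.7% | 5.4% |
| 5% | 20.0% | 14.3% |

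These are chances that the true count sits exactly one event above a pass. They measure fragility only.

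**Step 3: effect if some related SAEs were judged unrelated**

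Suppose each related SAE is counted with probability s, with at most one per patient. The counted number is then Binomial(n, p·s). For n = 80, P(pass) = P(X ≤ 3):

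| True rate p | s = 1 | s = 0.9 | s = 0.75 | s = 0.5 |
|---|---|---|---|---|
| 2% | 0.92 | 0.94 | 0.97 | 0.99 |
| 6% | 0.29 | 0.37 | 0.51 | 0.78 |
| 8% | 0.11 | 0.16 | 0.29 | 0.60 |

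For example, at p = 6% and s = 0.75 the effective rate is 0.06 × 0.75 = 4.5%, and the chance of passing rises from 0.29 to 0.51. At the prior rate of 2% the trial would probably pass either way. The documents give no value for s.

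**The case against.** The strongest reply is that 4.2.2 does name an assessor, so the endpoint is defined and the complaint is a preference for a different one. Site attribution is also reasonable as first-line reporting, and oversight does not rest on it alone:

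- Section 6.2.1.2 defines adverse events whether or not they are related to the intervention.
- Section 6.2.1.3 lists criteria for seriousness.
- The Grade III and IV limits in 6.1.1 state no relatedness filter.
- Adverse events go to the DMC throughout (7.5).

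Most of that stands. It confines the point to the endpoint rate and leaves the Grade III and IV stopping limits untouched. It does not explain why a plan with an independent adjudicating body bases a headline threshold on the site's call, or what happens when the two differ.

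A reader might infer several stronger claims that the documents do not support:

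- **An operator decides the outcome.** No section says that the site PI performs the index ESG. Section 5.5.1.1.2 shows involvement in re-tightening, and the rest is inference. The point needs only an unblinded site investigator.
- **The PI's judgement is final.** Section 4.2.2 does not say so. The gap is the missing link to 6.1.
- **The rate is biased downward.** Nothing shows under-attribution or variation between sites.
- **The probabilities in step 2 are the chance that a PI call flips the verdict.** They are not. They say nothing about how often the PI and the DMC would disagree, and a DMC decision on the marginal event would be just as pivotal.
- **DMC adjudication would be blinded.** No section says that the DMC is blinded. Relatedness to an endoscopic procedure can hardly be judged without knowing that the procedure took place.

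**Conclusion.** The point holds as a design weakness that should be corrected. The only numerical safety endpoint depends on relatedness as judged by an unblinded site investigator. The independent body charged with adjudicating adverse events has no stated bearing on that endpoint.

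The risk is structural. Its size is best put as the margin: a single event separates pass from fail, at 3 versus 4 among 80, or 7 versus 8 among an assumed 157. The margin moves to 4 versus 5 among 80 if the societal wording governs. The pass probabilities under under-attribution rest on assumed true rates and assumed counting shares, and they illustrate sensitivity rather than predict bias. Sample size, alpha, power and the primary efficacy analysis are unaffected.

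**What to change.** 1. In 4.2.2, replace the parenthesis that names the site PI with relatedness to the device or procedure as adjudicated by the DMC under 6.1.
2. In 6.1, state that DMC adjudication covers the relatedness of all SAEs and that its decision governs the endpoint.
3. Report the site PI's attribution as a secondary tabulation, so that any disagreement is visible.

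The cost is modest but not zero. The scope and process of case-level adjudication must be written down. The committee first meets after 25 ESG procedures and every four months after that, so its workload grows by the review of SAEs that it may already see. The reported rate may be somewhat less favourable. In return, a rate under 5% would rest on one independent standard across the nine sites.
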